14.2. Analysis of Endpoints

In keeping with our usual practice, we will obtain expert statistical advice from the Centre for Statistics in Medicine (or equivalent) for each specific task. A flow diagram detailing number of participants screened and randomised will be provided. Analysis of the OCT-derived primary and secondary endpoints (including angiography-derived) will be conducted offline in a blinded fashion. Summary statistics, including means, medians, and variances, will be calculated at each time point and for each type of data and group (e.g. baseline characteristics, parameters derived from OCT, angiography-derived coronary physiology). The distribution of the levels will be described. For each parameter an analysis of variance will be carried out.

An analysis evaluating for a between group difference in pre-stent thrombus volume will first use an 1-way ANOVA with a 2-sided equality test to assess for an overall trend. Post-hoc analyses exploring the following hypotheses i) retriever thrombectomy (Arm 3) is different to no thrombus modification (arm 1) and ii) retriever thrombectomy (Arm 3) is different to aspiration thrombectomy (Arm 2) will be performed using the Dunnett test. Control of the Type I error at 5% two-sided significance level due to multiple testing will be achieved using Dunnett's method.³⁶ Missing data for the primary analysis will be dealt with complete case analysis if data missingness is <10% (<3 cases per group). If missingness is higher, multiple imputation will be performed instead. Major adverse cardiac and cerebrovascular events will be analysed using proportions statistical testing (Fisher's exact or χ^2 tests), yet they represent an exploratory analysis.

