8. OBJECTIVES AND OUTCOME MEASURES

Objectives	Outcome Measures	Timepoint(s) of evaluation of this outcome measure (if applicable)
Primary Objectives		
Efficacy of thrombus burden reduction	Thrombus volume (mm ³) (OCT assessment)	Pre-stent
Safety of retriever thrombectomy	
Angiography-/OCT-defined device related target vessel complications, device deficiencyRate of major adverse cardiac and cerebrovascular events (MACCE)	Pre-stent In hospital 30 days 6 months
Secondary Objectives		
Efficacy of thrombus burden reduction	Thrombus area, flow area (mm ²) (OCT assessment)	Pre-stent
Efficacy of thromboatheroma reduction	Thromboatheroma area, flow area (mm ²) (OCT assessment)	Post-stent
Efficacy of stent implantation	Stent expansion & apposition (OCT assessment)	Post-stent
Angiographic success rate	TIMI flow, Myocardial Blush Grade, Angiography derived coronary physiology indices	Post-stent

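### Section 14.2 tests each secondary endpoint only by a three-arm ANOVA, with no retriever contrast and no retriever estimate

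*Combined protocol and SAP*

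**What the plan says.** Section 14.2 of the combined protocol and SAP promises descriptive summaries by group for every type of data and then states: "For each parameter an analysis of variance will be carried out". It names no contrast, significance level or adjustment there.

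The next paragraph turns to the primary endpoint: "An analysis evaluating for a between group difference in pre-stent thrombus volume will first use an 1-way ANOVA". It then names two comparisons, Arm 3 with Arm 1 and Arm 3 with Arm 2, and adds: "Control of the Type I error at 5% two-sided significance level due to multiple testing will be achieved using Dunnett's method". MACCE is to be compared by Fisher's exact or chi-squared tests, with the comment "yet they represent an exploratory analysis".

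The secondary objectives are in sections 4 and 8. Three of the four rows are worded as efficacy objectives, for example "Efficacy of thromboatheroma reduction", and the fourth concerns angiographic success. The outcome measures include "Thrombus area, flow area" before stenting and "Thromboatheroma area, flow area" after it.

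Section 9 describes the whole trial as exploratory, and the synopsis gives the phase as a device pilot.

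**The concern.** The secondary objectives ask what the retriever does compared with PCI alone and with aspiration. A one-way ANOVA on three arms asks whether any of the three means differ. These are different questions. The F-test can be significant because Arms 1 and 2 differ from each other, and it yields neither an effect size nor an interval for the retriever. If the retriever alone differs, which is what the plan expects, an F-test spread over all three arms is also somewhat less sensitive than the two comparisons of interest.

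At stake is how a significant secondary p-value is read. Under an efficacy heading it would naturally be taken as a retriever effect, although the planned test does not show that. A further, smaller matter is that 14.2 does not state the inferential status of the secondaries, while testing several of them.

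**Working it through.** **Count of secondary measures (section 8).** Pre-stent thrombus area and flow area: 2. Post-stent thromboatheroma area and flow area: 2. Stent expansion and apposition: 2. TIMI flow and Myocardial Blush Grade: 2. Physiology indices, plural and not listed: at least 1. Total: 2 + 2 + 2 + 2 + 1 = at least 9.

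**Plan's own figure.** There is none to reproduce, because the documents give no error rate or power for the secondaries.

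**Inputs.**
- 72 analysable patients in three arms (section 14.1): 72/3 = 24 per arm, residual df = 3 × 24 − 3 = 69.
- Level 0.05 for each ANOVA. This is an assumption, since the ANOVA sentence gives none.
- Standardised effect from the primary endpoint in 14.1: 0.33 × 9.6 / 5.1 = 3.168 / 5.1 = 0.62 SD. Using it for the secondaries is an assumption.
- Normal data. This is also an assumption, and a poor one for the two ordinal grades.

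**Does a significant F-test involve the retriever?** For each simulated trial, compute the F statistic and the two contrasts |mean of Arm 3 − mean of Arm j| / √(2s²/24), for j = 1, 2. Compare the larger contrast with the two-sided Dunnett critical value, about 2.26 by simulation. With all arms equal, about 26% of significant F-tests have neither retriever contrast significant.

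**Sensitivity if only the retriever differs by 0.62 SD.** The squared deviations of the three means from their average sum to (1/9 + 1/9 + 4/9) × 0.62² = (2/3) × 0.62². The noncentrality is 24 × (2/3) × 0.62² = 6.15, which gives the F-test on (2, 69) df a power of about 57%. By simulation, at least one Dunnett contrast is significant in about 62% of trials. (That 57% is below the 80% stated in 14.1 is a separate sample-size question. This point does not depend on it.)

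**Across endpoints.** Nine independent null tests: 1 − 0.95⁹ = 37.0%. With a common correlation between endpoints, by simulation:

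| Correlation | At least one significant ANOVA | At least one significant Dunnett contrast |
|---|---|---|
| 0 | 37% | 37% |
| 0.5 | 28% | 28% |
| 0.8 | 17% | about 17% to 18% |

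Replacing ANOVA by Dunnett contrasts therefore leaves this rate where it was: Dunnett adjusts across arms within an endpoint, not across endpoints. For comparison, Bonferroni over nine endpoints tests each at 0.05/9 = 0.0056, and 1 − (1 − 0.0056)⁹ is about 4.9%.

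**The case against.** The best defence is that this is a pilot. Section 9 calls the whole trial exploratory, the only stated hypothesis (section 7) concerns pre-stent thrombus volume, and nothing in the documents plans an efficacy claim from a secondary endpoint. Group summaries are promised, so a reader can see which arm differs. An ANOVA does not forbid follow-up contrasts, and 14.2 promises expert statistical advice for each task. In the case the plan expects, where only the retriever differs, almost every significant F-test would come with a significant retriever contrast, and the loss of sensitivity is about five percentage points.

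Much of this stands. A reader might infer, because 14.2 attaches the exploratory label to MACCE alone, that the secondaries are meant as confirmatory. The documents do not support that. MACCE sits under the primary safety objective, so there was a reason to mark it down, and section 9 covers the whole trial. At most the status of the secondaries is left unstated in 14.2.

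A reader might also infer that about half of significant secondaries would have nothing to do with the retriever. A figure of 48% does arise if aspiration differs from PCI alone by 0.62 SD and the retriever lies midway, but the plan does not expect that case. Sections 6 and 14.1 take aspiration as not shown to differ from no thrombus modification, and section 8's comparison is built around the retriever. That cited evidence concerns pre-stent thrombus volume, so it does not rule out a difference on post-stent measures, but the scenario remains an assumption.

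What does not stand is the idea that later advice or optional follow-up contrasts fill the gap. They would be chosen after the data exist, in a trial without masking of treatment, although image reading is blinded. Nor can the Dunnett sentence be taken as a general rule. It closes a passage whose two hypotheses concern pre-stent thrombus volume.

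**Conclusion.** The point holds as a mismatch between test and objective. As written, the secondary endpoints receive an omnibus test only, with no retriever contrast or estimate. The size is modest: about 26% of significant F-tests under the null show no significant retriever contrast, and sensitivity is about 57% against 62% when only the retriever differs. These figures rest on 24 analysable per arm, normal data, a 5% level and, for the second, an effect of 0.62 SD borrowed from the primary endpoint.

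Multiplicity is a minor clarification. The chance of at least one false positive among nine unadjusted tests, about 17% to 37%, is not a figure from the documents. It depends on an assumed correlation between 0.8 and 0 and on treating all nine measures as normal; more physiology indices would raise it. In an exploratory trial with no planned secondary claim, stating the status of these endpoints is enough.

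**What to change.** In section 14.2, limit the ANOVA sentence so that it no longer governs the secondary endpoints, and add text to this effect:

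- *Each continuous secondary endpoint will be compared between Arm 3 and Arm 1 and between Arm 3 and Arm 2. Differences will be reported as estimates with Dunnett-adjusted simultaneous 95% confidence intervals.*
- *TIMI flow and Myocardial Blush Grade will be compared for the same two contrasts by an ordinal or rank-based method*, with the method named.
- *Secondary endpoints are exploratory and are not adjusted across endpoints.*

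Listing the physiology indices at the same time would fix the number of tests. If a claim from a secondary is wanted after all, the order of testing has to be set in advance, because the contrasts alone do not control error across endpoints.

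The cost is wording only, with no new patients or data. The small downside is that Arm 1 and Arm 2 are no longer formally compared on the secondary endpoints. The group summaries already planned would still show that difference descriptively.

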One of the reasons why thrombus-aspiration catheters failed to remove thrombotic debris in STEMI can be related to the inability of the devices to actually interact with the clot. In the coronary artery the clot develops on top of an ulcerated/ruptured plaque, meaning that the bulk of the clot is often in an eccentric position, eventually protruding towards the centre of the lumen. An additional element that must be taken into account is the disproportion between the vessel lumen-cross-section-area (which can potentially be filled with thrombus) and the aspiration-opening area at tip of the aspiration catheter. If an average size coronary artery (diameter: 3.0 – 3.5 mm) is considered, the vessel lumen-cross-section-area can range from 7.06 to 9.61 mm². Since the aspiration-opening area at tip of the aspiration catheter is on average 0.9-1.0 mm², that means that the thrombectomy device technically covers (on average) from 9.4 to 14.2% of the vessel lumen-cross-section-area. In a larger caliber vessel (for example large ectatic right coronary arteries) this ratio becomes even more unfavourable. As the caliber of the vessel increases, its “theoretical” ability to contain large thrombus-burden increases proportionally, meaning that

Clinical Trial Protocol Template version 15.0
CONFIDENTIAL

© Copyright: The University of Oxford and Oxford University Hospitals NHS Foundation Trust 2019

Page 10 of 57

paradoxically the currently available aspiration devices become less effective in those cases when they would be required to work at their best.

Another element to account for poor performance of the current aspiration-catheters is the “guidewire bias effect”. This is a direct consequence of 1) the coronary arteries not being straight tubes, but having bends and curves and 2) of the thrombectomy-catheter sliding over an angioplasty-guidewire during the procedure. In a curved tube, like the coronary artery, the position of the wire can actually bias the aspiration device away from the clot. The “guidewire bias effect” can be minimally influenced by the operator. For this reason a clot-removal device that could interact with the whole vessel-lumen cross section area (and thus with the whole clot) and whose mode action is not affected by coronary artery caliber and by “guidewire bias effect” would be desirable and likely to be more effective in removing thrombus in STEMI patients.

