10.2. Inclusion Criteria

- Male or Female, aged 18-90 years.
- pPCI patient with ST elevation myocardial infarction.
- Angiographic criteria:
 - ◊ TIMI 0/1 flow at presentation
 - ◊ Angiographic thrombus score ≥ 4
 - ◊ Vessel diameter at site of occlusion ≥ 3.0 mm (measured by quantitative coronary angiography)

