14. STATISTICS

14.1. Number of participants

Based on estimates from previously published work^{9,34} and our stipulation for inclusion of patients with high thrombotic burden, we anticipate a mean pre-stent thrombus volume of 9.6mm³ with a standard deviation estimate of 5.1 mm³ in the standard of care arms. Since this is the first pilot of stent retriever in acute coronary syndromes there is no previous published work that can inform on the expected pre-stent thrombus volume reduction with retriever thrombectomy. We have therefore hypothesised a 33% reduction in mean pre-stent thrombus volume. Using a 1-way pairwise ANOVA with a 2-sided equality, accounting for 2 pairwise comparisons with an α of 0.05, a sample size of 72 patients would have 80% power to detect a 33% reduction in pre-stent thrombus volume with retriever thrombectomy.³⁵ The approach that was used accounts for two pairwise comparisons. Indeed, for one such comparison a sample size of n=48 (n=24 for Arm 1 and 24 for Arm 3) would maintain the desired α of 0.05 and β of 0.2. Given that aspiration thrombectomy was not shown to differ from no thrombus modification,⁹ a sample size of n=48 (n=24 for Arm 2 and n=24 for Arm 3) would maintain the desired α of 0.05 and β of 0.2 for this comparison. The overall sample size is therefore increased by a further n=24 patients for the aspiration thrombectomy group. This leads us to n=72 patients required to show a 33% reduction in pre-stent thrombus burden with a power of 80%. Assuming 12.5% of patients will not have analysable OCT imaging, we plan to enrol 81 patients (n=27 in each group) to ensure the study remains adequately powered.

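### The primary ANOVA omits vessel diameter, which is measured in every eligible patient before randomisation; adding it is a cheap change that may recover some precision, probably only a little

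*Combined protocol and SAP*

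**What the plan says.** Section 14.2 sets the primary analysis: "An analysis evaluating for a between group difference in pre-stent thrombus volume will first use an 1-way ANOVA with a 2-sided equality test". Arm 3 is then compared with Arm 1 and with Arm 2 by Dunnett's method, described as "Control of the Type I error at 5% two-sided significance level due to multiple testing". Each other parameter also gets an analysis of variance. No covariate or transformation is named, and sections 11.3 and 11.4 name no stratification factor for randomisation.

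Section 10.2 requires a vessel diameter of at least 3.0 mm at the occlusion site, "measured by quantitative coronary angiography", with no upper limit. Sections 11.4 and 11.6 place the eligibility check before randomisation.

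Section 6 gives the link to the outcome: "As the caliber of the vessel increases, its “theoretical” ability to contain large thrombus-burden increases proportionally". Section 8 lists secondary endpoints that are cross-sections of the same vessel: "Thrombus area, flow area (mm ²) (OCT assessment)".

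**The concern.** The QCA diameter is a true baseline value. It exists in all three arms and allocation cannot affect it. If it predicts thrombus volume, the variance it explains stays in the error term of the planned ANOVA, and both contrasts are less precise than they could be. The same holds for the thrombus and flow areas, which depend more directly on vessel size. Lumen area is 7.07 mm² at 3.0 mm and 12.57 mm² at 4.0 mm, so eligible vessels can differ a good deal.

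The more obvious covariate, thrombus volume on the Stage 2 OCT, is not available for Arm 3 v Arm 1. Section 11.6 treats that scan as the pre-stent measurement in Arm 1, so there it is the endpoint itself. QCA diameter can serve both contrasts.

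What is at stake is power in a small trial. With 24 to 27 patients per arm and no stratification by vessel size, chance differences in calibre between arms add noise to the comparison.

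**Working it through.** **Inputs (section 14.1).** "we anticipate a mean pre-stent thrombus volume of 9.6mm³ with a standard deviation estimate of 5.1 mm³ in the standard of care arms". "We have therefore hypothesised a 33% reduction in mean pre-stent thrombus volume". Two-sided 5% for two comparisons, 24 evaluable patients per arm. The target difference is 0.33 × 9.6 = 3.168 mm³, which is 3.168 / 5.1 = 0.621 SD.

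**The plan's own figure.** For one two-sided comparison at 5% and 80% power, n per arm = 2 × (1.960 + 0.842)² × (5.1 / 3.168)² = 40.7, so 41. The stated 24 per arm does not reproduce. At 24 per arm a single unadjusted comparison has 57.6% power (normal approximation).

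**Power of the planned contrasts.** The two-sided Dunnett critical value for two comparisons and three arms of 24 is 2.258 (69 df). The noncentrality is 0.621 × √(24/2) = 2.152. The noncentral t gives 46.2% power per contrast.

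**Power with one covariate.** Let ρ be the within-arm correlation of diameter with thrombus volume. The residual SD is 5.1 × √(1 − ρ²). One df is lost (68 df, critical value 2.259). Chance imbalance in the covariate inflates the variance by about 1 + 1/(72 − 5) = 1 + 1/67. So the noncentrality is 2.152 / [√(1 − ρ²) × √(1 + 1/67)].

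| ρ (assumed) | Noncentrality | Power | Change (points) |
|---|---|---|---|
| 0 | 2.14 | 45.5% | -0.7 |
| 0.2 | 2.18 | 47.2% | +1 |
| 0.3 | 2.24 | 49.6% | +3 |
| 0.4 | 2.33 | 53.1% | +7 |
| 0.5 | 2.47 | 58.4% | +12 |

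The results are the same for Arm 3 v Arm 1 and Arm 3 v Arm 2. The noncentrality breaks even where 1 − ρ² = 1 / (1 + 1/67), so ρ² = 1/68 and ρ is about 0.12. Simulation of 20,000 trials per value agrees: about 46% unadjusted, and about 47%, 49% and 58% adjusted at ρ = 0.2, 0.3 and 0.5. If all 27 per arm were evaluable, power would be about 51% unadjusted, 55% at ρ = 0.3 and 64% at ρ = 0.5.

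**What ρ might be.** The documents do not say. The plan's coefficient of variation (CV) for volume is 5.1 / 9.6 = 0.531. Suppose volume is diameter to some power times an independent factor.

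- *Linear in diameter:* ρ = CV of diameter / 0.531. For assumed diameter SDs of 0.26 to 0.57 mm, ρ is about 0.14 to 0.27 and the gain is under 3 points.
- *Proportional to lumen area (diameter squared):* the same SDs give ρ of about 0.28 to 0.56. Values near 0.5 need the wide end of that spread.
- *Diameters spread evenly over 3.0 to 3.5 mm*, the average-vessel range in section 6: SD = 0.5 / √12 = 0.144, CV = 0.144 / 3.25 = 0.044. Then ρ is about 0.08 (linear) or 0.17 (area), and the gain is under 1 point.
- *Measurement error:* an assumed error of 0.2 mm on an SD of 0.26 mm shrinks ρ by 0.26 / √(0.26² + 0.20²) = 0.79. That takes 0.14 to 0.11 and 0.28 to 0.22.

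**Chance imbalance in calibre.** It moves an arm difference with SD ρ × 5.1 × √(2/24): 0.44 mm³ at ρ = 0.3 and 0.74 mm³ at ρ = 0.5. These are 14% and 23% of the 3.168 mm³ target.

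**The case against.** The strongest case against is that no loss of power is shown. A reader might infer from section 6 that the plan forgoes a known and sizeable amount of power. The text does not support that. It speaks of theoretical capacity, and it says that capacity rises in proportion to calibre, which is the linear case with a gain under 3 points. The endpoint is thrombus remaining after a balloon has restored flow, and after thrombectomy in Arms 2 and 3. The planned mean of 9.6 mm³ would fill only 9.6 / 9.61 = 1.0 mm to 9.6 / 7.06 = 1.4 mm of vessel length at section 6's lumen areas, far below what the vessel could hold. Diameter is also read at an occluded site, where measurement error is plausible. This objection stands and limits the point to a possible gain.

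A reader might also infer that the unadjusted comparison is biased because an arm could receive larger vessels by chance. It is not: randomisation and the Dunnett error rate already allow for chance imbalance. Only precision is affected.

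Section 6 also suggests that aspiration works less well in larger vessels, so the slope on diameter may differ by arm. That does not invalidate a common-slope model as an estimate of the average difference, but it makes the calculated gain less certain.

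Finally, section 10.2 requires a threshold to be checked, and no section says that the continuous diameter is recorded. The cost is therefore slightly more than a change of wording.

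**Conclusion.** The point holds as a low-cost improvement. The primary model leaves out a baseline value that the eligibility check already requires and that the protocol gives a reason to think prognostic. On the plan's inputs, the effect on power per contrast runs from -0.7 points (ρ = 0) to +12 points (ρ = 0.5). A gain of 0 to 3 points is the more likely range if thrombus scales linearly with calibre. Larger gains need scaling with lumen area and a wide spread of diameters, and the documents establish neither.

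Adjustment should not be read as a remedy for the sample size. The unadjusted 46% reflects the fact that 24 per arm does not follow from section 14.1's inputs. That is a separate problem. Even a single comparison at 5% without Dunnett would need ρ of about 0.64 to reach 80% power at 24 per arm.

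**What to change.** Before any comparison by arm, amend section 14.2 as follows:

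- Make the primary model a linear regression of pre-stent thrombus volume on arm plus continuous pre-randomisation QCA diameter.
- Apply Dunnett's method to the adjusted Arm 3 v Arm 1 and Arm 3 v Arm 2 differences.
- Use the same covariate for the OCT area endpoints: pre-stent thrombus and flow areas, and post-stent thromboatheroma and flow areas.
- Include it as a predictor if multiple imputation is triggered.
- Report the unadjusted ANOVA and Dunnett results as a sensitivity analysis.
- Name the continuous diameter on the CRF, or state that it will be read from the stored pre-randomisation angiogram.

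The cost is one degree of freedom, worth about 0.7 points of power if diameter is unrelated to thrombus volume, and one recorded value per patient. No extra procedures or patients are needed.

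### The single-step Dunnett test in section 14.2 is valid, but a step-down version would add about 5 points of power per comparison at the same 5% familywise error

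*Combined protocol and SAP*

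**What the plan says.** Section 14.2 analyses pre-stent thrombus volume in two stages. The analysis "will first use an 1-way ANOVA with a 2-sided equality test to assess for an overall trend". Two comparisons follow: that "retriever thrombectomy (Arm 3) is different to no thrombus modification (arm 1"), and that retriever thrombectomy "is different to aspiration thrombectomy (Arm 2) will be performed using the Dunnett test". On multiplicity it says: "Control of the Type I error at 5% two-sided significance level due to multiple testing will be achieved using" Dunnett's method, with a reference to the 1955 paper. No step-down version is mentioned, and the section does not say whether the ANOVA must be significant before the comparisons are made.

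Section 14.1 gives the planning inputs: a "mean pre-stent thrombus volume of 9.6mm³ with a standard deviation estimate of 5.1 mm³ in the standard of care arms", and "We have therefore hypothesised a 33% reduction in mean pre-stent thrombus volume". It treats aspiration as no different from standalone PCI, and states 80% power with 72 analysable patients (24 per arm), enrolling 81 (27 per arm). It adds: "The approach that was used accounts for two pairwise comparisons". Power is described for each comparison separately. No figure is given for the chance that both succeed.

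**The concern.** With single-step Dunnett, each comparison is judged against the same adjusted critical value, whatever the other one shows. With only two hypotheses, that is stricter than familywise control requires. Once the larger |t| has passed the Dunnett value, the only hypothesis still open is the other comparison. By the closed-testing principle it can then be tested at the unadjusted two-sided 5% level, and the familywise error stays at 5%.

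The step-down rule rejects everything that the single-step rule rejects, and sometimes more. In a trial with 24 analysable patients per arm, the difference affects how likely the retriever is to be shown different from a given comparator, and from both.

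**Working it through.** **Inputs (section 14.1).** Control mean 9.6 mm³, SD 5.1 mm³ and a 33% reduction, so δ = 0.33 × 9.6 = 3.168 mm³ and δ/SD = 3.168/5.1 = 0.621. Arms 1 and 2 are taken as equal, with 24 analysable per arm. From section 14.2: two-sided 5% familywise error over two comparisons.

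**The plan's own figure.** The standard error of a difference is 5.1 × √(2/24) = 1.472, so δ/SE = 2.152. By the normal approximation, power per comparison is:

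- unadjusted two-sided 5%: Φ(2.152 − 1.960) = 57.6%;
- two-sided 2.5% (Bonferroni): Φ(2.152 − 2.241) = 46.4%.

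Neither reproduces the stated 80%. By n = 2 × SD² × (z_α + z_β)²/δ², 80% power needs 41 per arm unadjusted or 50 with Bonferroni. Dropping the factor 2 from the Bonferroni formula gives 24.6, which may be where 24 came from; that is an inference. The gain from step-down must therefore be measured from the true starting point of about 46%.

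**The two rules.** With 24 per arm there are 3 × 23 = 69 degrees of freedom. The exact two-sided Dunnett critical value (two comparisons, correlation 0.5) is 2.258, and the unadjusted t value is 1.995.

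- Single-step: reject each comparison if its |t| > 2.258.
- Step-down: reject the larger |t| if it exceeds 2.258; only then reject the other if its |t| > 1.995.

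**Power**, from 1,000,000 simulated trials per scenario with normal data and pooled three-arm variance:

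| | Single-step | Step-down |
|---|---|---|
| 24 per arm: each comparison | 46.2% | 50.7% |
| 24 per arm: both | 29.9% | 39.0% |
| 24 per arm: at least one | 62.4% | 62.4% |
| 27 per arm: each comparison | 51.4% | 56.2% |
| 27 per arm: both | 35.1% | 44.7% |
| 27 per arm: at least one | 67.8% | 67.8% |

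The rows agree with each other, since P(at least one) = 2 × P(each) − P(both). At 24 per arm this is 2 × 46.2 − 29.9 = 62.5 for single-step and 2 × 50.7 − 39.0 = 62.4 for step-down. The per-comparison gain is half the gain in winning both: (39.0 − 29.9)/2 ≈ 4.5 points.

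**Familywise error of step-down, 24 per arm.** Under the global null it is 4.99%. With Arm 3 equal to Arm 2 but different from Arm 1, it is 3.8% when the Arm 1 effect is as planned, 4.9% when that effect is doubled, and 5.0% when it is five times as large.

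**Role of the ANOVA.** If a significant F test were required first, the step-down chance of winning both would hardly move (39.0% to 38.9%), but the chance of at least one win would fall from 62.4% to 57.2%.

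**Sensitivity at 24 per arm (effects assumed here, not taken from the plan).**

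- Aspiration itself reduces volume by 10%: power against aspiration goes from 23.1% to 28.1%, and both from 17.2% to 24.1%.
- Aspiration reduces it by 15%: both goes from 11.5% to 17.0%, and Arm 3 v Arm 1 from 46.2% to only about 47%.
- The retriever reduces it by 20% and aspiration by nothing: both goes from 7.5% to 11.4%.

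**The case against.** The strongest reply is that nothing here is wrong. Single-step Dunnett is a standard method for two comparisons with a common arm, and it delivers the 5% control that section 14.2 promises. That stands: a reader might infer an error in the plan, and the documents do not support that.

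A reader might also take 30% as the trial's chance of success. The documents do not support that either. Section 14.1 powers each comparison separately, section 14.2 calls the comparisons post hoc and exploratory, and nowhere is success defined as winning both. On the plan's own footing the gain is about 5 points per comparison, and the chance of at least one significant result does not change.

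Nor is the change free. Step-down adds a rejection only when the smaller |t| lies between 1.995 and 2.258. The single-step simultaneous interval is the difference ± 2.258 × SE, so in every such trial it includes zero. On the planning inputs this happens in about 9% of trials (39.0 − 29.9). Single-step keeps tests and intervals in agreement, which has value in a pilot with no earlier estimate of the effect. This objection stands as a real but limited cost: the interval can still be reported and the mismatch explained.

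Finally, step-down does not cure the shortfall in power. That also stands. About 51% is still far below 80%, and the sample size is a separate and larger matter.

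**Conclusion.** The point holds as a cheap improvement to a valid plan. At the same 5% two-sided familywise error, step-down Dunnett raises power per comparison from about 46% to 51%, and the chance of winning both from about 30% to 39%, with 24 analysable per arm. If all 27 per arm are analysable, the figures are 51% to 56% and 35% to 45%. The chance of at least one significant comparison is unchanged, at about 62% with 24 per arm and 68% with 27.

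These figures rest on the plan's mean, SD and 33% reduction, equal Arms 1 and 2, a common SD and normal data. Thrombus volume may be skewed, and the gain in points is smaller if the retriever's effect is smaller or if aspiration removes some thrombus. That step-down never rejects less than single-step does not depend on these assumptions.

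**What to change.** Before the primary outcome is analysed, replace the multiplicity sentence in section 14.2 with text to this effect:

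- The two comparisons (Arm 3 v Arm 1, Arm 3 v Arm 2) are tested by the step-down Dunnett procedure. The larger |t| is compared with the two-comparison Dunnett critical value. Only if it is significant is the other compared with the unadjusted two-sided 5% t critical value. Both use the pooled three-arm variance.
- The initial one-way ANOVA is descriptive and does not gate these tests.
- Single-step Dunnett simultaneous confidence intervals are reported for both comparisons. If the second comparison is significant only through the step-down rule, the report says that its simultaneous interval includes zero, and why.

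Section 14.2 switches to multiple imputation when missingness is not below 10%, and section 14.1 expects 12.5% unanalysable OCT. The text should therefore also say how the two critical values are applied to the pooled imputation results.

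The cost is a few sentences, with no extra patients or data and no change to the endpoint or error rate. The choice has to be fixed in advance, because a switch made after the results are known would not be credible.
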